7.7 Research Samples

Research samples will be collected and shipped to the University of Pennsylvania for processing and storage, or processed at the local site and shipped to the University of Pennsylvania or the Children's Hospital of Philadelphia for storage. Research samples will be coded to maintain patient confidentiality and may be stored indefinitely for use in research, including in pursuit of the exploratory endpoints described in this protocol. Subjects will be asked to provide their consent to allow any biological samples collected as part of this study or collected during their enrollment period in this study, but for purposes outside of the study, to be used for laboratory research purposes, including genetic sequencing studies. Subjects will also be given the option to consent to allow any biological samples from their past medical procedures to be used for laboratory research purposes, including genetic sequencing studies.

7.8 Genetic Testing

As part of the exploratory objective, genetic testing may be performed on subject's biological samples. Such genetic testing would be strictly exploratory in nature. Samples will be used to study the genetic information that may be involved in Castleman disease, and efficacy or failure of sirolimus. Clinically significant results of genetic testing may be disclosed to the subjects at the discretion of the treating physician.

7.9 Safety Evaluations

Enrolled subjects will be carefully monitored throughout the study by study staff, with particular attention to known sirolimus AEs (See **Section 12.1 Risks** for details). Safety will also be assessed by changes in laboratory parameters, vital signs, and physical examinations. If any safety concerns arise, the licensed site investigators will promptly inform the Lead Principal Investigator and the Data Safety Monitoring Board (DSMB). The DSMB members will meet at preestablished times and as safety concerns arise to review the safety and clinical assessment data.

7.10 Concomitant Therapies

Corticosteroids (stable dose) and best supportive care are allowed throughout the course of the Intervention Phase. No additional systemic therapies directed at treating iMCD are permitted during the Intervention Phase.

8 Statistical Plan

This trial is a Phase II study of the efficacy and mechanism of action of sirolimus in anti-IL-6 blockade refractory iMCD. The trial is designed to rule out a therapy that has little or no biological activity in the examined patient cohort, a treatment-refractory population. The minimal acceptable level of activity is $\geq 20\%$. A common dose and dosing schedule will be employed for all subjects. An interim analysis will be conducted after 14 subjects have completed the Visit 9 intermediate assessment. If no responses are observed in these first 14 subjects, then the probability(response probability $\geq 20\%$) < 0.05, and the trial should be terminated. If at least one response is observed, additional subjects may be enrolled to increase the degree of precision of the standard error, to a total of 24 evaluable subjects.

The statistical considerations for this study were developed to answer the two overall research questions:

- Does sirolimus have activity in the treatment population? The only placebo controlled clinical trial in iMCD (NCT01024036) reported a 0% response in placebo. We have access to the historic data and plan to apply the study's endpoints, as applicable, as a benchmark for this trial, recognizing that some of the enrollment criteria were more stringent than those of this trial, and standard of care for iMCD may have changed since the first patient was enrolled into NCT01024036 (March 2010). We propose a maximum of up to 24 total evaluable patients with an interim analysis after 14 patients have completed the Visit 9 intermediate assessment. If no patients demonstrate a positive CBR response at the Visit 9 assessment, then it will be determined that sirolimus is unlikely to have activity in the study population. If one or more patients demonstrate a positive CBR, then additional patients may be enrolled in order to better estimate the response rate. Upon study completion, primary and secondary endpoints will be analyzed to determine if sirolimus has activity in the treatment population. Assessments will be based on the binary (yes/no) CBR criteria and continuation on drug, the continuous variable (0-16) CHAP disease activity scoring system, and the modified Cheson response criteria. Given the aggressive nature of the disease, historic data and preliminary nature of this trial, a placebo arm is not included in this study. The null hypothesis is that the intervention will have 0% activity.
- What is the mechanism of action by which sirolimus is efficacious in alleviating lymph node enlargement and clinical symptoms in iMCD? Cellular and molecular research assays will be performed to analyze changes in cell populations and signaling molecules between baseline and time points following sirolimus administration. Comparison will be made with paired t-tests and post-hoc corrections for multiple comparisons, as appropriate.

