3.1.2 Intervention Phase

Adult subjects will receive an oral sirolimus loading dose of 5 mg/m², rounded to the nearest mg (day 1). Loading dose may be lower at the discretion of the prescribing physician. Starting on day 2, adult subjects will receive oral sirolimus daily at 2.5 mg/m²/day (rounded to the nearest mg), adjusted as needed to a target trough level of 10-15 ng/mL. Pediatric subjects will not receive a loading dose, and daily dosing will be at 2 mg/m²/day (rounded to the nearest mg), adjusted to achieve a target trough level of 5-15 ng/mL. Subjects will remain on treatment for 12 ± 1 month. The period between the loading dose/first dose and the last treatment define the "Intervention Phase". Patients will continue to receive standard of care treatment during the Intervention Phase consistent with the requirements of **Section 6.6, Subject Withdrawal**. Subjects will undergo regular Intervention Phase visits (**Section 6.2, Intervention Phase**). The licensed site investigator will be ultimately responsible for all treatment decisions, including when to initiate rescue therapy (**Section 6.4, Rescue Therapy**).

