3.2.2 Secondary Study Endpoints

The secondary endpoints of this study will be:

- The proportion of patients achieving a positive CBR response (**Section 7.6**, **Efficacy Evaluations**) at 3, 6, and 9 months ± 2 weeks following administration of sirolimus loading dose. Assessments will be compared to those obtained at the Baseline Visit.
- The proportion of patients that remain on study drug for the duration of the study.
- The proportion of patients that indicate that they are currently receiving sirolimus at the end of the Follow Up Phase.
- Disease activity, as measured by the CHAP scale, at 3, 6, and 9 months ± 2 weeks and 12 ± 1 month. Assessments will be compared to those obtained at the Baseline Visit.
- Disease activity, as measured by MCD-related Overall Symptom Score as measured by 34 outcome measures (Section 7.6, Efficacy Evaluations), at 3, 6, and 9 months ± 2 weeks and 12 ± 1 month. Assessments will be compared to those obtained at the Baseline Visit.
- The proportion of patients achieving a lymph node response, following the modified Cheson response criteria (**Section 7.6, Efficacy Evaluations**). Assessments will be compared to those obtained at the Baseline Visit.

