6.4 Rescue Therapy

At the discretion of the licensed site investigator, a subject can be removed from the trial due to disease progression or serious AE (SAE). Decision to remove a subject from the trial and which rescue therapy(ies) to administer rest solely with the licensed site investigator.

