7.6 Efficacy Evaluations

The below measures will be used to assess the efficacy of the study intervention and determine if the subject meets criteria for a CBR. All comparisons are against those obtained during the Baseline Visit:

Positive response: Relative to baseline, improvement in at least one of the below criterion without worsening of any single criterion other than hemoglobin on two consecutive study visits.

Negative response: Relative to baseline, worsening of any single criterion other than hemoglobin on two consecutive site visits or failure to achieve improvement for any criterion.

	Hemoglobin	Fatigue	Anorexia	Fever and night sweats	Weight	Lymph node size
Improvement	≥2 g/dL increase without transfusions	≥1 grade decrease by NCI CTCAE version 4.0, May, 2009	≥1 grade decrease by NCI CTCAE version 4.0, May, 2009	≥2°C decrease in fever or return to normal body temperature (37°C) or improvement in night sweats, as assessed by licensed site investigator	≥5% increase not due to increase in new or existing edema	≥25% decrease bi-dimensionally in size of largest lymph node, as measured using Cheson criteria (Appendix 15.2)
Worsening		≥2 grade increase by NCI CTCAE version 4.0, May, 2009	≥2 grade increase by NCI CTCAE version 4.0, May, 2009	≥2°C increase in fever or worsening in night sweats, as assessed by licensed site investigator	≥5% decrease (weight loss not due to decreased edema)	≥25% increase bidimensionally in size of largest lymph node, as measured using Cheson criteria (Appendix 15.2)

The below table provides the CHAP score, which will be used to assess the efficacy of the study intervention. All comparisons are against those obtained during the Baseline Visit:

Score:	0	1	2	3	4
CRP (mg/dL)	<1	≥1, <5	≥5, <10	≥10, <20	≥20
Hemoglobin (g/dL)	≥12	<12, ≥10	<10,≥8	<8	Transfusion dependent
Albumin (g/dL)	≥3	<3,≥2.5	<2.5, ≥2	<2, ≥1.5	<1.5
Performance Score (ECOG)	0	1	2	3	4

The below table provides the modified Cheson response criteria, which will be used to assess the efficacy of the study intervention. Unless otherwise specified, all comparisons are against those obtained during the Baseline Visit:

Complete Response (CR)	All index lesion(s) must have regressed to normal size (≤1.0 cm in		
	their greatest transverse diameter. No new sites of		
	lymphadenopathy >1.5 cm in longest dimension.		
Partial Response (PR)	≥50% decrease in sum of the products of the greatest diameters		

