8.2 Secondary Endpoints

The secondary endpoints for this study are (1) the proportion of patients achieving a positive response based on the CBR criteria during intermediate assessment time points, (2) the proportion of patients that remain on study drug for the duration of the study, (3) the proportion of patients that indicate that they are currently receiving sirolimus at the end of the Follow Up Phase, (4) changes in the patient's disease activity, as measured by the CHAP score during intermediate and final assessment time points, (5) changes in the patient's disease activity, as measured by MCD-related Overall Symptom Score as measured by 34 outcome measures during intermediate and final assessment time points and (6) lymph node response, as measured by the Cheson criteria during intermediate and final assessment time points. Comparisons will be made against values obtained during the Baseline Visit.

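### Section 8 counts continuation on drug as evidence of activity, but the on-study measure requires no improvement and the stated 0% null is not a valid reference for it

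*Combined protocol and SAP*

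**What the plan says.** The opening of Section 8, under the question whether sirolimus has activity in the treated population, says: "Upon study completion, primary and secondary endpoints will be analyzed to determine if sirolimus has activity in the treatment population". The next sentence names the inputs: "Assessments will be based on the binary (yes/no) CBR criteria and continuation on drug", then CHAP as a 0 to 16 score and the modified Cheson criteria. The paragraph closes with the only null in the plan: "The null hypothesis is that the intervention will have 0% activity". Sections 8 and 8.4 take the 0% from the placebo response rate in the one placebo-controlled iMCD trial.

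Two secondary endpoints measure continuation. Section 3.2.2 has "The proportion of patients that remain on study drug for the duration of the study". Section 8.2 repeats it and adds "the proportion of patients that indicate that they are currently receiving sirolimus at the end of the Follow Up Phase". Neither definition contains a disease outcome.

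On staying or leaving:
- Section 3.1.2 sets the default: "Subjects will remain on treatment for 12 ± 1 month".
- Section 7.6 makes "failure to achieve improvement for any criterion" enough for a negative CBR, but attaches no withdrawal to it.
- Section 6.6 lists progressive disease and use of another systemic iMCD therapy among the reasons for discontinuation. Section 6.4 leaves removal for progression to the investigator's discretion.
- Section 5.2 describes treatment beyond 12 months for patients who have improved, at their physician's discretion.

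**The concern.** Under Section 8 a subject with 12 months of unchanged disease is a failure on one basis for the activity conclusion (CBR) and a success on another (continuation). The plan gives no rule for combining the bases, and no null, benchmark or threshold for continuation.

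A response rate of 0% is a coherent null for CBR if one accepts the historic placebo figure. It is not a reference for retention, because subjects can stay on a drug that does nothing for them. In an open-label single-arm trial, retention also reflects tolerability, the lack of alternatives and willingness to remain. Here the drug is supplied free (Section 13.3) and other systemic iMCD therapy is barred during the Intervention Phase (Section 7.10).

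What is at stake is the final interpretation: a high retention figure could be cited as activity beside a low CBR rate, and the wording of Section 8 would permit it.

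**Working it through.** **1. The plan's own figure.** Section 8 stops the trial if none of 14 subjects responds, because a response probability of 20% or more would then be unlikely. The smallest n with (1 − 0.20)^n < 0.05 is 14: 0.8^13 = 0.055 and 0.8^14 = 0.044. The figure of 14 reproduces. It concerns the CBR response probability only; continuation does not enter it.

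**2. Inputs to the two measures, side by side.**

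| Subject on study drug at 12 months | CBR (Section 7.6) | On-study continuation (Section 3.2.2) |
|---|---|---|
| Improved, no qualifying worsening | Positive | Counted |
| Unchanged | Negative | Counted |
| Qualifying worsening, but not withdrawn | Negative | Counted |

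The second and third rows separate the measures. The third can occur because removal for progression is discretionary.

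**3. Chance that an inactive drug gives a continuation proportion above 0%.** Let s be the probability that a subject stays on an inactive drug for the full period. The documents give no value, so s is an assumption and a range is shown. N = 24 is the maximum evaluable number (Section 8.4). With independent subjects:

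P(at least one continuer) = 1 − (1 − s)^24

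| s (assumed) | Expected continuers, 24s | (1 − s)^24 | P(at least one) |
|---|---|---|---|
| 2% | 0.5 | 0.616 | 38% |
| 5% | 1.2 | 0.292 | 71% |
| 10% | 2.4 | 0.080 | 92% |
| 20% | 4.8 | 0.005 | 99.5% |

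**4. How large s must be before a non-zero result is close to certain.** Solving 1 − (1 − s)^24 = t gives s = 1 − (1 − t)^(1/24). For t = 0.95, s = 11.7%; for t = 0.99, s = 17.5%.

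**5. Denominator.** Section 8.6 includes dosed subjects in the analyses for each visit they complete. Sections 6.6 and 8.4 allow subjects who drop out to be replaced. The denominator of the continuation proportion is therefore not fixed. If subjects who stop early leave the denominator or are replaced, the proportion rises with no change in the drug's effect.

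**The case against.** The strongest reply is that nothing in the plan tests continuation. The primary endpoint is CBR (Sections 3.2.1 and 8.1), the interim rule uses CBR (Sections 8 and 8.5.2), and the only test against an external reference is CBR versus historic placebo (Section 8.5.1). Section 8.5 already prescribes counts and percentages for categorical variables. The sentence in Section 8 can be read as a loose list by type of variable; it even omits the Overall Symptom Score, which is a secondary endpoint. CBR and its 95% confidence interval must be reported, so a near-zero response rate would be visible. All of this stands, and it limits the point to the wording of the end-of-study conclusion. It does not remove it: Section 8 says these assessments determine activity, and it names continuation beside CBR.

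A reader might also infer four stronger things that the documents do not support.
- **That retention is tested against 0% or against the 20% minimum activity level.** Both figures refer to response, and no section applies either to continuation.
- **That nothing removes a non-responder.** Progression and use of another systemic iMCD therapy are listed reasons, the list in Section 6.6 is not exhaustive, and investigators may discontinue a subject at any time. Retention therefore carries some efficacy information. The gap is narrower: stable, unimproved disease triggers no mandatory withdrawal.
- **That the follow-up version has no link to outcome.** Section 5.2 describes continuing beyond 12 months for patients who improve. The endpoint itself still counts anyone who reports receiving sirolimus, and the follow-up call in Section 6.3.1 asks about continued use without tying it to response.
- **That a non-zero proportion is almost certain with no drug effect.** That needs s of roughly 12% to 17.5% or more, which is an assumption.

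**Conclusion.** The point holds in limited form. Section 8 makes continuation on drug a basis for the activity conclusion, although the on-study measure requires no improvement and the one stated null belongs to response. An inactive drug would be expected to yield a non-zero proportion. The chance of at least one continuer among 24 is 71%, 92% or 99.5% if s is 5%, 10% or 20%, and only 38% if s is 2%. These figures rest on the assumed s, on independent subjects and on 24 in the denominator. They show why 0% is not a usable reference for retention; they are not the error rate of any test in the plan. The primary analysis and the interim decision are unaffected. The correction is still worth making, because it costs little and removes a route by which retention could be presented as efficacy.

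**What to change.** In the opening of Section 8:
- Delete continuation on drug from the sentence that lists the bases for the activity conclusion.
- State that this conclusion rests on CBR, with CHAP and the modified Cheson criteria supportive. The deletion alone is not enough, because the preceding sentence lets all secondary endpoints, including both continuation proportions, determine activity.

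In Sections 8.2 and 8.5.1, say that both continuation proportions are reported descriptively as retention and tolerability. Use all dosed subjects as denominator, including those later replaced, and tabulate the reasons for stopping, which Section 6.6 already requires to be recorded. A composite of being on drug with a positive CBR at Visit 15 is not needed, since it adds little to the primary endpoint. No change to withdrawal or treatment rules is implied.

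The cost is protocol and SAP wording only, with no new data. The downside is that retention can no longer be quoted as evidence of activity.

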8.4 Sample Size and Power Determination

Up to 24 subjects may be evaluated under this study, with an interim analysis to be conducted after 14 subjects have completed the Visit 9 intermediate assessment. Additional subjects may be enrolled to increase the degree of precision of the standard error, to a total of 24 evaluable subjects. We anticipate enrolling up to 40 subjects to reach our goal of 24 evaluable subjects.

The difference between enrollment and evaluable accounts for potential subjects that may be deemed ineligible upon screening, or who drop out of the study but are replaced.

Our expected response rate is $\geq 20\%$ versus the null hypothesis of 0% response. The placebo response rate in the only placebo controlled, double blinded clinical trial in iMCD was 0%. Given these parameters, power analysis with type 1 error $\alpha = 0.05$ and power of 1- $\beta = 0.8$ provides a samples size of 14 to determine if sirolimus has activity; the drug will be considered not likely to have a $\geq 20\%$ activity if no responses are seen in the interim analysis.

Sample size was chosen based on (1) convenience and the logistical constraints of recruiting a rare disease population and (2) our intention to probe for a signal of response and understand sirolimus' mechanism of action.

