8.5.1 Efficacy Analysis

CBR will be used as the primary endpoint for assessment of treatment response. Response to drug will be summarized as CBR and its 95% confidence interval and tested using Chi-square (versus historic placebo control data). Difference in CBR in two different study sites will be summarized and compared using the Chi-square tests. Significance will be established at α =0.05.

The baseline covariates will be tested for association with CBR using logistic regression or two-sample t-test and the unadjusted p-values will be reported. When biomarkers are evaluated for association with CBR, we will perform logistic regression analysis for each marker adjusting for possible baseline covariates. The false discovery rate procedure will be used to adjust for multiple comparisons. As an exploratory analysis, if the CBR is not too low, we will also apply the random forest method to evaluate whether such biomarkers cab be predictive to CBR.

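### The stated null of 0% response cannot carry an alpha of 0.05, the chi-square named for the final analysis tests a different null on counts too small for it, and a significant result would not show that the plan's 20% minimum is met

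*Combined protocol and SAP*

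**What the plan says.** The opening text of Section 8 says: "The null hypothesis is that the intervention will have 0% activity". Section 8.4 repeats this as "Our expected response rate is $\geq 20\%$ versus the null hypothesis of 0% response", attaches a type I error of 0.05 and a power of 0.8, and arrives at 14 subjects. The maximum is 24 evaluable subjects.

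Section 8.5.1 describes the final analysis of the primary endpoint. The CBR rate is reported with a 95% confidence interval and "tested using Chi-square (versus historic placebo control data"), with significance at 0.05. Sidedness and continuity correction are not stated.

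Section 8 also sets a floor: "The minimal acceptable level of activity is" at least 20%. This figure is the design alternative in Section 8.4. It also drives the interim rule, under which no responses among 14 subjects at Visit 9 means that activity of 20% or more is considered unlikely. Nothing ties the 12-month result to it.

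For the historic placebo group, Section 8 reports a 0% response. It does not give the number of placebo subjects or say that the 0% was measured by CBR. It says only that the historic trial's endpoints will be applied where applicable.

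**The concern.** The null, the test and the minimum do not line up. A 0% null makes any response impossible, so no error rate can be controlled against it. The chi-square addresses a different hypothesis, and its result depends on a denominator that the documents do not give. With no responders in the historic group and few in this trial, the large-sample approximation behind chi-square is doubtful, and the unstated choice of continuity correction moves the threshold. Because the 20% minimum drops out after the interim, a p-value below 0.05 could be read as showing worthwhile activity when the estimate lies under the plan's own minimum.

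**Working it through.** **Inputs from the documents:** null 0%, alternative and minimum 20%, alpha 0.05, power 0.8, interim 14, maximum 24, historic placebo response 0%. **Assumed:** m = 20 to 60 historic subjects, none a CBR responder, two-sided 0.05, and all 24 subjects evaluable.

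**1. The plan's own figure.** With a true rate of 20%, P(0 of n) = 0.8^n. This is 0.0550 at n = 13 and 0.0440 at n = 14, so 14 is the smallest n at which zero responses has probability below 0.05. The interim number therefore reproduces. It does not follow from the stated null at 80% power. If one responder rejects, power is 1 − 0.8^n, which is already 0.832 at n = 8 and is 0.956 at n = 14. A small non-zero null would fit. With a null of 2% and at least 2 of 14 required, alpha is 0.031 and power is 1 − 0.8^14 − 14 × 0.2 × 0.8^13 = 1 − 0.044 − 0.154 = 0.802. The plan does not state such a null.

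**2. The literal 0% null at 24.** P(at least 1 responder | 0%) = 1 − 1^24 = 0, so 1/24 rejects with alpha equal to zero. The same criterion would be met with probability 1 − 0.99^24 = 0.214 at a true rate of 1%, and 1 − 0.95^24 = 0.708 at 5%.

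**3. The two-sample chi-square.** For r/24 against 0/m the uncorrected statistic is (24 + m) × r × m / [24 × (24 + m − r)], compared with 3.841. The smallest expected count is r × min(24, m) / (24 + m).

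- m = 20: r = 4 gives 44 × 4 × 20 / (24 × 40) = 3.67, not significant. r = 5 gives 44 × 5 × 20 / (24 × 39) = 4.70, significant. Smallest expected count: 5 × 20/44 = 2.3.
- m = 30: r = 3 gives 54 × 3 × 30 / (24 × 51) = 3.97, significant. Smallest expected count: 3 × 24/54 = 1.3.
- m = 60: r = 1 gives 2.53. r = 2 gives 84 × 2 × 60 / (24 × 82) = 5.12, significant. Smallest expected count: 2 × 24/84 = 0.6.

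Fewest responders of 24 for p < 0.05:

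| m (assumed) | Uncorrected | Yates | Fisher | Smallest expected count at uncorrected threshold |
|---|---|---|---|---|
| 20 | 5 | 6 | 6 | 2.3 |
| 26 | 4 | 5 | 4 | 1.9 |
| 30 | 3 | 5 | 4 | 1.3 |
| 40 | 3 | 4 | 3 | 1.1 |
| 50 | 2 | 4 | 3 | 0.6 |
| 60 | 2 | 3 | 3 | 0.6 |

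Every smallest expected count is well below the usual guide of 5. The continuity correction alone moves the threshold by one or two responders.

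**4. Against 20%.** The Clopper-Pearson limits are the 2.5% quantile of Beta(x, 25 − x) and the 97.5% quantile of Beta(x + 1, 24 − x). For 3/24 (12.5%) they are 2.7% and 32.4%. This result is significant by uncorrected chi-square at m = 30 and m = 40. The lower limit is 18.8% at 9/24 and 22.1% at 10/24, so it first exceeds 20% at 10/24.

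**The case against.** A reader might infer that the plan prescribes two rival final tests that give opposite answers. If one responder is set against the chi-square threshold for 20 to 60 historic subjects, the two differ with probability 0.21 to 0.84 at a true rate of 10%. The documents do not support that reading. No one-sample final test and no rule that one responder means activity appears anywhere. A chi-square against a fixed 0% cannot be computed because the expected number of responders is zero, so the two-sample comparison is the only computable test named. Section 8.4 puts the 0% null next to the 0% placebo rate, so it can fairly be read as shorthand for no better than placebo. The probabilities above would compare the planned test with one that the plan does not contain, on an assumed historic size.

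A reader might also infer that the 20% is never used. It is used, as the design alternative and in the 0/14 rule. The gap is confined to the final analysis.

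Finally, the trial is a screen for activity followed by estimation. Section 8.4 says that its size reflects convenience and the search for a signal. Such a design need not end with a superiority test against 20%. A 3/24 result that beats placebo with a wide interval is not a contradiction, and the planned interval shows the uncertainty. That stands, and it argues against a formal decision rule on the interval. It does not rescue the wording of the null, the choice of chi-square, or the silence on what a significant result says about the minimum.

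**Conclusion.** The point holds as a mismatch between the stated null and the test, and as an unsuitable test. The 0% null appears twice and cannot carry the stated alpha. The named test has a different null and rests on smallest expected counts of about 2.3 down to 0.6 at its own threshold. That threshold is 5 down to 2 of 24 uncorrected, and 6 down to 3 with Yates or Fisher. Significance can occur below the plan's 20% minimum, as with 3/24 at 30 to 40 historic subjects uncorrected. A lower confidence limit above 20% needs 10/24.

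The thresholds depend on the assumed 20 to 60 historic subjects, on none of them being a CBR responder, and on 24 evaluable subjects. The fault in the 0% null depends on none of these. The interim number of 14 is sound as a futility figure.

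**What to change.** - **Sections 8 and 8.4:** replace the 0% null with the hypothesis actually tested, that the CBR rate equals that of the historic placebo subjects.
- **Section 8.5.1, test:** replace chi-square for the primary comparison with a two-sided Fisher's exact test. State the number of historic subjects, and score them by the same CBR definition. If CBR cannot be derived for them, make the comparison supportive only, so that the primary result is the estimate with its interval.
- **Section 8.5.1, interpretation:** name the Clopper-Pearson method for the 95% interval. State that significance against placebo does not show that the 20% minimum is met, and that showing this would need a lower limit above 20% (10/24 or more). This is an interpretation statement, not a new success rule. It remains necessary under Fisher's test, because 3/24 is still significant at 40 historic subjects.

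The cost is wording, plus scoring the historic data for CBR. Fisher's test needs up to about one more responder than uncorrected chi-square. At a true rate of 20%, power falls from 0.540 to 0.344 with 20 historic subjects and from 0.967 to 0.885 with 60, and is unchanged with 26 or 40. The final claim becomes more modest.
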